11.0.5 Sponsor Responsibility for Reporting Adverse Events

All Adverse Events will be reported to regulatory authorities, IRB/IECs and investigators in accordance with all applicable global laws and regulations.

12.0 SAMPLE CALCULATION AND STATISTICAL ANALYSIS PLAN

The primary endpoint is overall immune-related objective response rate. We expect that similar to mismatch repair deficient patients, the immune-related objective response will be at or above 40% in patients with functional FA deficiency (FATSI negative), and less than 10% in patients without either homologous recombination repair deficiency or mismatch repair deficiency. Patients with mismatch repair deficiency will be excluded from this trial. Based on our prior screening data, we anticipate that close to 30% of patients with solid tumors, depending on tumor type will be FA functionally deficient.

We will utilize a two-stage phase II trial design to detect an iORR of at least 20% in the whole population tested vs. the null hypothesis that the true iORR is at most 5%, representing a response by chance alone, or other infrequent unknown mechanism. Specifically, we will test the null hypothesis $H_0: \text{iORR} \leq 5\%$ vs. $H_1: \text{iORR} \geq 20\%$ with 90% power and a Type I error rate of 10%. The alternative hypothesis of 20% iORR represents a weighted average of the anticipated 40% response in FATSI-negative patients and 10% response in FATSI-positive, assuming a 3 to 7 ratio of these patient groups. Interim analysis requires that at least two of the first 20 evaluable patients enrolled have an objective response. If this occurs, we will accrue 19 additional patients for a total of 39. Overall rejection criterion of the null hypothesis is observing at least 4 responses.

The proposed two-stage design was chosen instead of the Simon Optimal or Minimax design because it has a larger first stage enrollment and thus a higher expected number of FATSI-negative patients in the interim analysis. Total enrollment of 39 patients is only slightly greater than that of the Simon designs but has the advantage of increasing the expected number of FATSI-negative patients. Additionally, the proposed design has a higher early stopping probability under the null hypothesis. The following table summarizes these operating characteristics.

Table 10:

Design	First stage enrollment	Expected		Total enrollment	Total expected FATSI-patients	Actual α	Power	Expected study size
		FATSI-patients, 1 st stage	PET					
Optimal	12	4	0.54	37	11	0.093	90.2%	23
Minimax	18	5	0.40	32	10	0.072	90.1%	26
Proposed	20	6	0.74	39	12	0.099	91.7%	25

FATSI: FATSI negative. PET: Probability of early termination at completion of first stage enrollment. α : Probability of false positive finding (type 1 error, falsely rejecting the null hypothesis).

Protocol Version: 15

We will analyze the paraffin embedded tumors of the participating patients for FA functional deficiency. Analysis will be conducted in batches.

We will report the 90% confidence interval estimates of iORR both overall and by FATS1 status using the exact method (Clopper-Pearson). We note, however, that the planned study is too small for a well-powered comparison given that we expect only 12 FATS1-negative patients. Instead, variation in iORR by FATS1 status will be assessed by considering the one-sided 95% lower confidence limit (95%LCL) for the difference. The following table illustrates the 95%LCL for several possible study outcomes in which iORR is higher in FATS1- patients. Taking the second rows as an example, an observed increase in iORR for FATS1-negative patients of 34.3%, based on 5 out of 12 FATS1- responders compared with 2 out of 27 FATS1+ responders, provides 95% confidence that the true increase for patients with FA deficient tumors is at least 9.4%, suggesting that further study of Pembrolizumab in FA deficient patients is warranted.

Table 11:

iORR					
FATS1-		FATS1+		Difference	95%LCL
5 / 12	41.7%	1 / 27	3.7%	38.0%	13.8%
5 / 12	41.7%	2 / 27	7.4%	34.3%	9.4%
5 / 12	41.7%	3 / 27	11.1%	30.6%	5.1%
4 / 12	33.3%	1 / 27	3.7%	29.6%	6.5%
4 / 12	33.3%	2 / 27	7.4%	25.9%	2.1%
4 / 12	33.3%	3 / 27	11.1%	22.2%	-2.3%

The incidence of severe (NCI CTCAE v4 grade 3+) adverse events or toxicities will be described. Kaplan-Meier curves will be used to estimate the distributions of overall survival and immune-related progression-free survival (iPFS). Point estimates and 2-sided 95% confidence intervals will be reported for selected times using Greenwood's variance and the log-log transform method. This will include the 20-week iPFS for purposes of comparison with the literature.

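### Does it matter that the 20% alternative, described as a weighted average of 40% and 10% at 3:7, works out at 19%?

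*Combined protocol and SAP*

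**What the plan says.** Section 12.0 of the combined protocol and SAP plans a "two-stage phase II trial design to detect an iORR of at least 20% in the whole population tested", against a null rate of at most 5%, with 90% power and a 10% type I error rate. Twenty evaluable patients enter the first stage. Two or more responses allow 19 further patients, and four or more responses among 39 reject the null. Table 10 gives this design a probability of early termination of 0.74, an actual type I error of 0.099, a power of 91.7% and an expected size of 25.

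The origin of the 20% is given in one sentence: "The alternative hypothesis of 20% iORR represents a weighted average of the anticipated 40% response in FATSI-negative patients and 10% response in FATSI-positive", with the two groups in a 3 to 7 ratio. Earlier in the same section the component rates are looser. The FATSI-negative rate is put at or above 40%, and the other is "less than 10% in patients without either homologous recombination repair deficiency or mismatch repair deficiency". The FATSI-negative share is described as close to 30% and dependent on tumour type. After Table 10, the section notes that a comparison by FATSI status would be underpowered, "given that we expect only 12 FATS1-negative patients".

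**The concern.** All three inputs to the weighted average are stated, and they give 19%, not 20%. Nothing in the section marks the 20% as rounded. This is the only derivation offered for the target of the primary hypothesis, so a reader who repeats it finds a sentence that does not compute.

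The one-point difference also straddles the power requirement: the design has 91.7% power at 20% but 89.7% at 19%. If 19% is what the investigators expect, the trial appears to fall slightly short of its own specification, and the chance of stopping wrongly after the first stage is 8.4% rather than 6.9%. At stake would be whether 39 patients and the thresholds of 2 and 4 are adequate for the effect the trial was built to find.

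**Working it through.** **Inputs, all from section 12.0 unless noted.** Null 5%; alternative 20%; first stage 20 patients, continue at 2 or more responses; second stage 19 patients, reject at 4 or more of 39; component rates 40% and 10%; weights 0.3 and 0.7; expected split 12 and 27 (Tables 10 and 11). The screening prevalence of 28.7% comes from Table 1 in section 4.1.

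**Formula.** Enrolment is not selected on FATSI status, so each patient is treated as an independent draw with response probability *p*. With X1 ~ Bin(20, *p*) and X2 ~ Bin(19, *p*):

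P(reject) = P(X1 = 2) × P(X2 ≥ 2) + P(X1 = 3) × P(X2 ≥ 1) + P(X1 ≥ 4)

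**Step 1: reproduce Table 10.**

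- *p* = 5%: 0.1887 × 0.2453 + 0.0596 × 0.6226 + 0.0159 = 0.0993 (table: 0.099). Early termination P(X1 ≤ 1) = 0.736 (table: 0.74). Expected size 20 + 19 × (1 − 0.736) = 25.0 (table: 25).
- *p* = 20%: 0.1369 × 0.9171 + 0.2054 × 0.9856 + 0.5886 = 0.9165 to rounding (table: 91.7%).

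The type I error and power of the Optimal and Minimax rows also reproduce (0.0935 and 0.9024; 0.0721 and 0.9015). Table 10 is therefore right for the hypotheses it describes.

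**Step 2: the weighted average.** 0.3 × 40% + 0.7 × 10% = 12% + 7% = 19%.

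**Step 3: power at the averages the plan's own figures imply.**

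| Source of the average | Calculation | *p* | Power |
|---|---|---|---|
| Hypothesis as stated | none | 20% | 91.7% |
| Expected 12/27 split | (12 × 0.40 + 27 × 0.10)/39 = 7.5/39 | 19.2% | 90.1% |
| 3 to 7 ratio | above | 19.0% | 89.7% |
| Table 1 prevalence | 0.287 × 0.40 + 0.713 × 0.10 | 18.6% | 88.8% |

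At 19% the terms are 0.1545 × 0.9004 + 0.2175 × 0.9818 + 0.5439 = 0.8965. Power reaches 90% at *p* = 19.16%. The shortfall at 19% is 90 − 89.65 = 0.35 percentage points.

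**Step 4: how far the inputs must move to give exactly 20%.** Changing one at a time: a FATSI-negative rate of (0.20 − 0.07)/0.3 = 43.3%; or a FATSI-positive rate of (0.20 − 0.12)/0.7 = 11.4%; or a FATSI-negative share of (0.20 − 0.10)/(0.40 − 0.10) = 33.3%. The first fits the plan's wording, which makes 40% a floor. The second does not, because 10% is a ceiling. The third is 3.3 points above the nominal 30%.

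**Step 5: dependence on the model.** If the mix is held at its expected counts (6 and 14 in the first stage, 6 and 13 in the second) with rates of 40% and 10%, power is 91.6%. This is a conditional illustration only, since the actual mix will vary.

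**The case for a change.** The best argument for a correction is that the sentence is false as written, that it is the sole support for the primary target, and that one clause would put it right. The cushion is also thin: any true rate below 19.16% takes power under 90%, and the prevalence in Table 1 gives 88.8%. The more favourable 12/27 figure owes something to rounding too, because 0.3 × 39 is 11.7, not 12. The fixed-mix 91.6% cannot be relied on, since patients are enrolled without regard to FATSI status and the assay is run in batches; the model with a single mixture rate is the natural one, and it reproduces Table 10.

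All of that stands as arithmetic. What does not follow is that a claim in the plan is wrong. The 90% requirement is attached to a rate of 20%, where it is met with 1.7 points to spare; setting it against power at 19% compares a target for one rate with performance at another. Nor is 19% a firmer number than 20%. With the FATSI-negative rate a floor, the FATSI-positive rate a ceiling and the prevalence approximate, the true average may lie on either side of both. Adding power for other assumed subgroup rates would be a separate sensitivity exercise, not a correction of this slip.

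**Conclusion.** The arithmetic point is correct: the stated inputs give 19%, and 20% is best read as an unstated rounding to a conventional design target. It is a clerical slip without consequence. Across the averages that the plan's own figures support, 18.6% to 20%, power runs from 88.8% to 91.7%. That spread is small beside the uncertainty in the component rates. The type I error, which rests on the 5% null, is unaffected.

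Rewording the sentence would change neither the hypotheses, the 20/39 sample size, the thresholds of 2 and 4, Tables 10 and 11, nor any conclusion the trial could reach. No change to the plan is called for. This rests on exact binomial calculation with independent patients sharing one mixture response rate, and on reading the 90% power requirement, as the section writes it, as applying at 20%.

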12.1 Expansion Cohort

At the conclusion of the accrual as specified above, an expanded cohort of 10 patients with the diagnosis of metastatic or recurrent endometrial carcinoma or endometrial sarcoma will be enrolled. These patients need tissue availability and documentation of microsatellite low or stable. (see Section 6.1.1 for inclusion/exclusion criteria). All clinical benefit measure parameters and correlates will be obtained, as per the other patient. No additional statistical inferences, other than comparison between FATS1 positives and negatives in terms of clinical outcome will be done.

Protocol Version: 15

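### The overall response-rate interval ignores the stage-1 stop, so its upper limit is slightly too low at the smallest successful results (4/39 and 5/39)

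*Combined protocol and SAP*

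**What the plan says.** Section 12.0 tests a null overall immune-related response rate of at most 5% against an alternative of at least 20%, in two stages. At the interim, "Interim analysis requires that at least two of the first 20 evaluable patients enrolled have an objective response"; if so, 19 more patients are added, for 39 in all. At the end, "Overall rejection criterion of the null hypothesis is observing at least 4 responses". Table 10 gives this design an early-termination probability of 0.74 (under the null), an actual alpha of 0.099, power of 91.7% and an expected size of 25.

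The same section then fixes the reporting of the primary endpoint: "We will report the 90% confidence interval estimates of iORR both overall and by FATS1 status using the exact method (Clopper-Pearson"). Neither Section 12.0 nor any other section adjusts this interval for the interim stop.

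**The concern.** The test and the interval for the primary endpoint rest on different sampling models. Table 10 counts the stage-1 stop. The Clopper-Pearson interval treats 39 patients as a sample size fixed in advance.

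A futility stop moves probability from higher final counts to low results. Trials that stop at 0/20 or 1/20, some of which would have recovered to five or more responses had they gone on, now end below 4/39. The lower tail is then larger than the fixed-sample calculation assumes, and an upper limit placed at a fixed-sample 5% is too low. The place where this matters is a trial that only just succeeds: 4/39 is the smallest count that rejects the null. What is at stake is the accuracy of the reported error bar, not the go/no-go decision.

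**Working it through.** **Inputs (Section 12.0).** Stage 1 has n1 = 20 and stops at 0 or 1 response. Stage 2 adds n2 = 19, so N = 39. The null is rejected at 4 or more responses. The interval is two-sided 90%, so 5% per tail.

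**Model.** For true rate p, the trial stops with probability P(stop) = (1−p)^20 + 20p(1−p)^19. It continues and ends with s responses in 39 with probability P(s) = Σ over x ≥ 2 of Bin(x; 20, p) × Bin(s−x; 19, p).

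**Reproducing Table 10.** At p = 0.05, P(stop) = 0.736, the rejection probability ΣP(s) over s ≥ 4 is 0.0993, and the expected size is 20 + 19 × (1 − 0.736) = 25.0. At p = 0.20 the rejection probability is 0.9165. All agree with Table 10. A single-stage rule of 4 or more in 39 would give alpha 0.129 and power 0.967, so Table 10 does count the stop.

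**Tail at the planned upper limit U.** The two-stage lower tail is P(stop | U) + Σ P(k | U) for k = 2 to s.

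- 4/39, U = 21.95%: stopped trials 0.0070 (0/20) + 0.0396 (1/20) = 0.0466; continuing trials with 2, 3 or 4 responses 0.0311; total 0.0777.
- 5/39, U = 25.09%: stopped trials 0.0239; continuing trials with 2 to 5 responses 0.0383; total 0.0622.

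The fixed-sample tail is 0.0500 in both cases. These are real miss rates: 0/20 and 1/20 have planned upper limits of 13.9% and 21.6%, so for a true rate just above 21.95% they miss it as well.

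**Tail at the planned lower limit.** The two-stage upper tail is 3.8% at 4/39 and 4.4% at 5/39. Both are below 5%, so the lower limit is conservative.

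**Two-stage interval.** Under stage-wise ordering (every stopped trial ranks below every continuing trial), solve lower tail = 0.05 for the upper limit and upper tail = 0.05 for the lower limit.

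| Result | Planned 90% interval | Two-stage lower tail at planned upper limit | Stage-wise exact 90% interval |
|---|---|---|---|
| 2/39 | 0.9% to 15.3% | 17.7% | 1.8% to 21.7% |
| 3/39 | 2.1% to 18.7% | 11.0% | 2.7% to 22.3% |
| 4/39 | 3.6% to 22.0% | 7.8% | 3.9% to 23.8% |
| 5/39 | 5.2% to 25.1% | 6.2% | 5.4% to 25.9% |
| 6/39 | 6.9% to 28.1% | 5.5% | 7.0% to 28.5% |
| 7/39 | 8.7% to 31.1% | 5.2% | 8.8% to 31.2% |

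From 4/39 up, ordering by the Clopper-Pearson upper limit gives the same two-stage limits. At 2/39 and 3/39 it does not, and the tail shown there is not pure non-coverage, because the planned interval at 1/20 still covers those rates.

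**Coverage of the whole planned procedure** (Clopper-Pearson on 20 if stopped, on 39 otherwise):

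| True rate | Coverage | Chance of ending at 4/39 or 5/39 |
|---|---|---|
| 5% | 96.2% | 8.8% |
| 10% | 96.4% | 28.3% |
| 20% | 93.9% | 11.7% |
| 22% | 89.0% | 7.7% |

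Over true rates from 0.5% to 60%, coverage is below 90% only at about 22.0% to 23.2% and 25.1% to 25.4%. At 22%, 7.7% of trials have an upper limit below the truth and 3.4% a lower limit above it. The stage-wise interval covers 91.9% at 22%, and its minimum over the same range is 90.4%.

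**One-sided bound.** Setting the two-stage upper tail to 0.10 gives a lower bound of 3.64% at 3/39 and 5.01% at 4/39. The bound passes 5% exactly where the rule starts to reject. The fixed-sample equivalent at 4/39 is 4.55%.

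**The case against.** The strongest reply is that almost nothing follows from this. Coverage is above nominal at both design rates, the shortfall elsewhere is about one percentage point, and no planned decision uses the upper limit: the rule is a count. All of that stands, and it is why the point is minor.

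It can also be said that the excess comes from stopped trials. Of the 7.77% at 4/39, 4.66 points are stops at 0/20 or 1/20, and given continuation to stage 2 the lower tails are 3.3% (4/39) and 3.9% (5/39). That is correct. The point therefore holds for unconditional coverage only. This is the usual standard, and the one Table 10 uses for alpha and power.

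Two stronger readings are tempting, and neither is supported:

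- A reader might infer that the plan wrongly excludes the 20% target at 2/39 and 3/39. The planned upper limit misses a true 20% in only 2.6% of trials (0/20 1.15%, 2/39 0.20%, 3/39 1.23%), within the 5% allowed. Clopper-Pearson also needs no ordering. The ordering question arises only with a two-stage replacement: stage-wise limits there include 20%, while ordering by the Clopper-Pearson upper limit gives 14.9% and 17.6%, which exclude it.
- A reader might blame the ignored stop for the planned interval at 4/39 still containing the rejected 5%. The stop is only part of the cause. The interval leaves 5% per tail beside a one-sided 10% test, and the two-stage two-sided interval (from 3.9%) also contains 5%.

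**Conclusion.** The point holds in limited form. As a description of the two-stage trial, the planned upper limit for the overall response rate is too low at 4/39 (tail 7.8%) and 5/39 (tail 6.2%), against a nominal 5%. The shift needed is 1.8 points at 4/39, 0.8 at 5/39 and under 0.4 from 6/39 up. Minimum coverage is about 89.0% against 90%.

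The documents do not support any claim that the interval is unreliable in general, that the interim or final rule is wrong, or that the stated error rates are affected. Table 10's figures for the design reproduce. Calling Clopper-Pearson the exact method names a procedure; it does not claim exact two-stage coverage.

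The conclusion assumes that the stop at 0 or 1 in 20 is followed as written, that exactly 39 patients are analysed if the trial continues, and that coverage is judged over all trials, including those that stop. Severity: minor.

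**What to change.** In Section 12.0, for the overall response rate in the 39-patient main cohort, replace Clopper-Pearson with the exact two-stage 90% interval and name stage-wise ordering. Add its one-sided 90% lower bound, which agrees with the rule of four or more responses. Keep Clopper-Pearson for the FATSI subgroups, labelled as descriptive. Section 12.1 already limits inference from the expansion cohort ("No additional statistical inferences, other than comparison between FATS1 positives and negatives in terms of clinical outcome will be done"), so naming the 39-patient cohort only makes the scope explicit.

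The cost is SAP wording and a few lines of code, with no change to design, sample size or conduct. Results at 4/39 and 5/39 get a slightly higher upper limit. At 2/39 and 3/39 the upper limits rise from 15.3% and 18.7% to 21.7% and 22.3% and no longer exclude 20%; the team should accept this knowingly and before the overall result is known. The two-sided interval will still contain 5% at 4/39, which is why the one-sided bound should be reported beside it.

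If the team prefers to keep Clopper-Pearson overall, the minimum is a sentence saying that it ignores the stage-1 stop and is descriptive.

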5.3.2 Biomarker Research and Correlative Endpoints

FATSI Assessment. The main hypothesis of this trial is that pembrolizumab has clinically meaningful antitumor activity in solid tumor patients with functional deficiency in the Fanconi Anemia (FA) pathway in their tumors. We will be performing The FATSI assay, as previously described [16,17], in archived paraffin embedded tumors of enrolled patients to assess for functional deficiency. We hypothesize that a FATSI negative assay will be associated with a better response rate, that those patients able to form FANCD2 repair foci. However, we will not preselect patients to this trial based on FATSI negativity.. The non-selection approach will avoid bias in case we observe a higher than expected rate of antitumor response or PFS in our treated patients independent of FATSI status. The results will be exploratory in nature, as there will not be sufficient statistical power (see Statistics Section).

Tissue and Blood DNA sequencing. We will obtain a blood sample at the beginning of the trial, prior to pembrolizumab therapy in participating patients in order to obtain cell free DNA for mutation analysis, and will also perform tumor DNA sequencing in archival tissue material in an attempt to search for the gene abnormalities responsible for the FA functional deficiency when relevant, as well as an estimation in mutation load. We will refer for family genetic counseling those patients for which germline deficiency is a consideration, either by family history or by results of the above tests. The correlative methods to be utilized are not validated for germline mutation and cancer risk analysis, but whenever a consideration is raised by results genetic counseling with validation analysis is the best ethical approach.

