7.2 Subject Replacement Strategy

We anticipate enrollment of 39 patients for which tumor and toxicity assessments following pembrolizumab administration can be made. We will replace patients enrolled for which clinical trial discontinuation was performed prior to any administration of pembrolizumab or those for which pembrolizumab is discontinued due to acute hypersensitivity reactions during the first administration of pembrolizumab. An attempt will be made to assess tumor response in all enrolled patients as specified in the protocol. However, patients experiencing clinical deterioration after two doses of pembrolizumab, will be considered treatment failures and will count as tumor progression. These patients will not be replaced.

We are also expecting that 30% of the patients enrolled will be negative on the FATS1 assay, which will be conducted in batched analyses.

See section 6.1.1 and 12.0.1 for expansion cohort.

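### The plan names no method for the one-sided 95% lower limit on the FATSI difference. Table 11 uses the unpooled Wald limit, which misses 6.8% of the time at the planned 40% vs 10%

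*Combined protocol and SAP*

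**What the plan says.** Section 12.0 names Clopper-Pearson for the response rates themselves: "We will report the 90% confidence interval estimates of iORR both overall and by FATS1 status using the exact method (Clopper-Pearson". It names Greenwood's variance with a log-log transform for the survival estimates. For the contrast between FATSI groups it says only: "Instead, variation in iORR by FATS1 status will be assessed by considering the one-sided 95% lower confidence limit (95%LCL) for the difference". Table 11 illustrates this with six outcomes at 12 and 27 patients. The worked row (5/12 vs 2/27) is read as a result that "provides 95% confidence that the true increase for patients with FA deficient tumors is at least 9.4" percent, and the text takes this to suggest that further study in FA-deficient patients is warranted.

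The planning rates are in the same section: "anticipated 40% response in FATSI-negative patients and 10% response in FATSI-positive, assuming a 3 to 7 ratio". They are also given as a range: "the immune-related objective response will be at or above 40% in patients with functional FA deficiency (FATSI negative), and less than 10% in patients". The second group in that range is patients free of both kinds of repair defect. Section 7.2 leaves the split to chance: "We are also expecting that 30% of the patients enrolled will be negative on the FATS1 assay, which will be conducted in batched analyses". Section 5.3.2 sets the status of the FATSI comparison: "The results will be exploratory in nature, as there will not be sufficient statistical power".

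**The concern.** The limit on the difference is the only inferential summary planned for the FATSI contrast in the main cohort, and that contrast is the trial's second hypothesis. Clopper-Pearson is a one-proportion method and cannot fill the gap. With no method named, the choice stays open after the data are seen, and it changes the answer: for the plan's own 5/12 vs 2/27 example, Agresti-Caffo gives 8.9%, Wald 9.4%, Newcombe 10.9% and Miettinen-Nurminen 11.3%.

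The plan also reads the size of the limit as a minimum true gain held with 95% confidence. With 12 patients in one group and a response rate near 10% or lower in the other, the normal approximation behind a Wald limit may not deliver that level.

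**Working it through.** **Inputs (Section 12.0).** Group sizes 12 and 27 (39 in total, 12 expected FATSI-negative); planned rates 40% and 10%; one-sided 95%, so z = 1.645.

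**Step 1: reproduce Table 11.** The unpooled Wald limit is d - z*sqrt(p1(1-p1)/n1 + p2(1-p2)/n2). For 5/12 vs 2/27, d = 0.4167 - 0.0741 = 0.3426. The standard error is sqrt(0.02025 + 0.00254) = 0.1510. The limit is 0.3426 - 1.645*0.1510 = 9.4%, as printed.

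The Agresti-Caffo limit uses the same formula after adding one responder and one non-responder to each group. For the same row, 6/14 - 3/29 = 0.3251, the standard error is sqrt(0.01749 + 0.00320) = 0.1438, and the limit is 8.9%.

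| Outcome | Printed | Wald | Agresti-Caffo | Newcombe |
|---|---|---|---|---|
| 5/12 vs 1/27 | 13.8 | 13.80 | 12.87 | 15.28 |
| 5/12 vs 2/27 | 9.4 | 9.43 | 8.85 | 10.86 |
| 5/12 vs 3/27 | 5.1 | 5.12 | 4.89 | 6.61 |
| 4/12 vs 1/27 | 6.5 | 6.46 | 6.38 | 8.89 |
| 4/12 vs 2/27 | 2.1 | 2.06 | 2.34 | 4.41 |
| 4/12 vs 3/27 | -2.3 | -2.27 | -1.63 | 0.11 |

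Wald matches all six entries. Pooled Wald (12.4 in the second row), continuity-corrected Wald (3.4), Miettinen-Nurminen (11.3) and the two limits tabulated above do not.

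**Step 2: exact miss rate.** The miss is the sum of Bin(12, p1) x Bin(27, p2) probabilities over all 13 x 28 outcomes in which the limit exceeds p1 - p2.

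| True rates | Wald | Agresti-Caffo |
|---|---|---|
| 40% vs 10% | 6.83% | 3.99% |
| 40% vs 8% | 5.2% | not needed |
| 40% vs 5% | 5.09% | 2.52% |
| 50% vs 10% | 6.41% | 2.72% |
| 50% vs 5% | 6.48% | 3.03% |
| 40-60% by 2-10%, average (peak) | 6.9% (10.7%) | 3.2% (4.6%) |
| 20-60% by 2-15%, average (peak) | 5.8% (10.7%) | 3.3% (4.8%) |

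The grids use 1-point steps. On the first, Wald exceeds 5% at 97% of points; on the second, at 66%. Agresti-Caffo never exceeds 5% on either.

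**Step 3: chance of a limit above 0 when the groups do not differ.** At common rates of 5, 10, 15, 20, 25 and 30%:
- Wald: 0.6, 1.9, 3.3, 4.3, 5.1 and 5.6%.
- Agresti-Caffo: 1.2, 3.4, 4.3, 4.7, 5.2 and 5.6%.
- Newcombe: 3.7, 5.2, 6.0, 6.3, 6.1 and 6.0%.

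**Step 4: the split is random.** For every split from 8/31 to 17/22, the miss at 40% vs 10% is 5.4-7.0% for Wald and 2.3-4.0% for Agresti-Caffo. Among simulated trials that pass stage 1 and reach 39 patients with a random 30% mix, it is 6.8% and 3.8%.

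**Step 5: outcomes stronger than those in Table 11.** Against 2/27, Wald and Agresti-Caffo give 17.5 and 15.8 at 6/12, 26.1 and 23.1 at 7/12, 35.4 and 30.9 at 8/12, and 45.4 and 39.2 at 9/12. Newcombe gives 17.7 at 6/12, above Wald, and 40.7 at 9/12, below it. At 7/12 the Newcombe limit is d - sqrt((p1 - l1)^2 + (u2 - p2)^2), where l1 and u2 are Wilson limits: 0.509 - sqrt(0.227^2 + 0.127^2) = 24.9%, also below Wald.

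**The case against.** The strongest case against concerns weight and the choice of remedy, and much of it stands.

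- **6.8% is a local high.** One outcome, 7/12 vs 1/27, carries 1.76 of the 6.83 points, and its limit (30.5%) is only half a point above the true 30%. The miss is 5.8% at 41% vs 10%, 5.2% at 40% vs 8% and 5.1% at 40% vs 5%. This stands for the single figure. It does not remove the 6.9% average over 40-60% by 2-10%, though that range rests partly on assumed ends.
- **A reader might infer that the printed limits are too high.** The material does not support this. Newcombe lies above Wald in all six rows, and even Agresti-Caffo is above it in two. Wald exceeds both only for stronger results, such as 7/12 or more vs 2/27.
- **A reader might infer that the plan invites false signals of a difference.** It does not at low common rates: Wald's chance of a limit above 0 is 1.9% at a common 10%, and Agresti-Caffo raises it to 3.4%.
- **Agresti-Caffo is conservative, not better calibrated.** Wald is nearer 5% at 68% of points on the 20-60% by 2-15% grid. This stands. The case for Agresti-Caffo is that its error at the expected rates is on the safe side.
- **No decision rule hangs on the limit.** The plan calls the comparison exploratory and too small for a well-powered test. That excuses low power. It does not excuse an unnamed method or a 95% label that is not met at the plan's own rates.

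**Conclusion.** The point holds as a minor one. The method is unnamed, Table 11 is unpooled Wald, and at 12 vs 27 that limit misses 6.8% at the planned 40% vs 10%. It averages 6.9% over 40-60% by 2-10%, so the stated 95% confidence is nearer 93% on average in the expected range. This assumes independent binomial responses and, for the average, the assumed 60% and 2% ends. The 40% vs 10% result does not depend on an exact 12/27 split.

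The point does not extend to the primary all-comer test, the Clopper-Pearson intervals or the survival estimates. Nor does it show that any printed Table 11 value is wrong for the method used.

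**What to change.** Before FATSI results are read, add one sentence to Section 12.0: the one-sided 95% lower limit for the difference in iORR (FATSI-negative minus FATSI-positive) is the Agresti-Caffo limit, adding one responder and one non-responder to each group, computed at the actual group sizes. State its miss (4.0% at 40% vs 10% with 12 and 27 patients) and its no-difference rates from Step 3.

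Change the last column of Table 11 to 12.9, 8.9, 4.9, 6.4, 2.3 and -1.6%, and the 9.4% in the worked example to 8.9%. No row changes sign.

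The cost is wording and one table column, with no extra patients. There are two downsides. The limit is conservative at the expected rates (average miss about 3.2%). Its chance of exceeding 0 under no difference is higher than Wald's at low common rates (3.4% vs 1.9% at 10%) and slightly above 5% at common rates of 25-30% (5.2% and 5.6%). At 40% vs 10% the chance of a limit above 0 rises slightly, from 64.2% to 66.7%.

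Newcombe at nominal 95% is less suitable, because its no-difference rate is 5.2-6.3% at common rates of 10-30%. Miettinen-Nurminen still misses 5.75% at 40% vs 10%.
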